### **TSCS Blood Pressure (BP) decision tree**

Intensity ramp starting at 10 mA and increasing at 10 mA intervals until:

**1. Intolerable to patient**

- a. If uncomfortable, but tolerable, lower increments to 5mA increase/interval

**2. Sustained BP response - 3 or more manual systolic BP within the target range:**

**MALES: systolic BP 110-120 mmHg; FEMALES: systolic BP 100-120 mmHg**

- a. At each mA interval a manual blood pressure is taken ~1 minute:
  - i. **IF:** systolic BP increases by 10 mmHg above baseline repeat BP recording
  - ii. **IF:** still 10 mmHg above baseline take a third BP recording.
  - iii. **IF:** still 10 mmHg - but < 100 mmHg (< 90 females mmHg) increase by 10 mA and repeat manual BP assessments.
  - iv. **IF:** still 10 mmHg - but < 110 mmHg (< 100 mmHg females) increase by 5 mA and repeat manual BP assessment.
  - v. **IF:** between 110-120 mmHg (100-120 mmHg females) stop intensity ramp and monitor BP for 10 minutes at that mA ramp.
  - vi. **IF:** only 1 or 2 readings that are 10 mmHg above baseline continue incremental ramp at 10 mA.
  - vii. **IF:** during the 10-minute assessment systolic BP drifts down to < 110 but > 100, continue ramp at 5 mA.
  - viii. **IF:** during the 10-minute assessment systolic BP drifts down to < 100, continue ramp at 10 mA.

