### Methods & Procedures:

We aim to compare stimulation parameters (frequency and amplitude, 1-ms pulses) using a monophasic waveform for different spinal segment sites to modulate BP. Sites for stimulation during a series of seated experiments will include 1) T 7/8; 2) T 9/10; 3) T11/12; and 4) L1/2, while beat-to-beat seated BP is continuously monitored and recorded in hypotensive individuals with SCI.

This study will take approximately 7-study visits, between 1-3 hours, per subject. Participants will be asked to arrive between 8:00 am and noon at the James J Peters VA Medical Center (JJP VAMC), after a normal breakfast and a good night sleep. The participants will be asked to not drink alcohol or caffeine 12 hours prior to their visit and there will be at least 3 days between study visits.

Approach: We will compare the electrode placement sites and amplitude during seated rest to modulate BP. We anticipate that BP responses will vary among the participants regarding the location of the electrode placement site and signal amplitude. Participants will visit the laboratory 8 times: visit 1): informed consent and medical intake to determine eligibility for enrollment in the study. Visits 2-8: amplitude (mA) mapping sessions at each electrode placement site (randomized), with continuous beat-to-beat BP monitoring at the finger arteriole and at 1-minute intervals at the brachial artery.

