Targeted Transcutaneous
Stimulation to Restore Autonomic
Cardiovascular Health in Veterans
with Spinal Cord Injury

NCT05180227

August 18, 2025

Statistical analysis plan:

The primary outcome variable will be systolic blood pressure. Data will be analyzed with a mixed-modeling approach to determine which stimulation parameters consistently yield increases in systolic blood pressure. Participant will be modeled as a random effect and stimulation characteristics as fixed effects including: cathodal stimulation site (T7/8, T9/10, T11/12, and L1/2); stimulation frequency (30, 60, 120 Hz); waveform (monophasic, biphasic, asymmetric biphasic); pulse width (40 - 1000 μ s); carrier frequency (0, 10kHz); and stimulation current (0–120mA). To quantify the effect size of each participant's optimal tSCS parameters, each participant's blood pressure response will be compared to baseline blood pressure to calculate Cohen's d and confidence intervals. All analyses will be performed using R software. The lme4 package will be used to perform the mixed-models analyses for the ratio-scale data. The ordinal package in R will be used to analyze the Likert-scale-type data. The 95% level of confidence will be used. We used the R software simr package for multi-level models for power calculations with fixed effects variables of waveform and electrode site. Given the number of repeated measurements of SBP in each participant, we anticipate having *95% power to detect <2-mm-Hg mean differences at the 95% level of confidence.

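### The decision tree lets the SBP response set how many readings each current step contributes, and the SAP has no per-step summary or session term to stop responding sessions being over-weighted

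*Protocol*

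**What the plan says.** The Protocol's TSCS decision tree (item 2a) sets the reading schedule:

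- Every step: "At each mA interval a manual blood pressure is taken ~1 minute".
- After a rise: "systolic BP increases by 10 mmHg above baseline repeat BP recording".
- If the rise persists: "still 10 mmHg above baseline take a third BP recording".
- If it does not: "only 1 or 2 readings that are 10 mmHg above baseline continue incremental ramp at 10 mA".
- If SBP is in the sex-specific target range: "stop intensity ramp and monitor BP for 10 minutes at that mA ramp".

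Items vii and viii provide for SBP falling back during that 10-minute period. Methods & Procedures adds two other SBP streams, "with continuous beat-to-beat BP monitoring at the finger arteriole and at 1-minute intervals at the brachial artery", and states that responses are expected to vary among participants by electrode site and amplitude.

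The SAP says "The primary outcome variable will be systolic blood pressure" and gives no device, time window or per-step summary. Participant is the only stated random effect; site and current are among the fixed effects. The power statement (95% power for differences under 2 mmHg) opens "Given the number of repeated measurements of SBP in each participant". Each participant's response at the optimal setting is to be compared with baseline as a Cohen's d.

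**The concern.** The number of readings at a step, and the time spent there, are consequences of the outcome being modelled. The minute-by-minute brachial and beat-to-beat finger data inherit the imbalance through time at the step, so choosing another stream does not remove it.

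A participant intercept removes differences between people. It does not remove differences between sessions (sites) within a person, and it does not discount a run of correlated readings taken during one high spell. If every reading enters the model, sessions that respond, or happen to drift upward, count for more. The study's purpose is to find which settings raise SBP consistently. At stake are the size of the stimulation effect, the ranking of sites with consistent and erratic responses, the false-positive rate, and a power claim built on the reading count.

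**Working it through.** **1. The stated power.** It cannot be reproduced, because no SD, intraclass correlation or number of readings is given. As a benchmark, take 12 participants, one within-person difference each, two-sided 0.05 (assumed), 95% power for 2 mmHg. The SD of the difference must be 2 × √12 / (1.960 + 1.645) = 6.928 / 3.605 = 1.92 mmHg, or about 1.75 with the t distribution. At SDs of 4, 6 and 8 mmHg, t-based power is 35%, 18% and 12%. The claim therefore leans on the repeated readings.

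**2. Readings per cell, from the tree.** No rise: 1. Unsustained rise: 2 or 3. Sustained in range: 3 + 10 = 13, if the hold is read once a minute. In a comparison of one flat and one held cell, the held cell supplies 13/14 = 93% of the readings instead of 50%.

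**3. Simulation of the tree.** From the documents: 12 participants, 4 sites, male thresholds, the step rules. Assumed: baseline mean 98, SD 6 mmHg; 5 baseline and 10 hold readings; reading SD 4 to 8; drift absent, or first-order autoregressive with SD 8 to 12 and correlation 0.5 to 0.95. The tree does not say what follows an SBP above 120, so any sustained SBP of 110 or more entered the hold. There were 250 trials per scenario, with a participant intercept.

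| Assumed truth | Quantity | All readings | First reading per step |
|---|---|---|---|
| Independent error, one common effect | bias, stimulation minus baseline, mmHg | 0.0 | 0.0 |
| Drift, true effect 0 or 0.1 mmHg/mA | same | +0.1 to +1.3 | -0.2 to -2.5 |
| Half the visits 0.2 mmHg/mA, half 0 | slope per 100 mA (true mean 10) | 12.4 to 15.3 | 5.2 to 7.4 |

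The zero in the first row is Wald's identity: a high reading triggers more readings, but under independence those are centred on the truth. Under drift they share the high spell. With no true effect, drift gave +0.1 to +1.1 mmHg over the whole assumed range and roughly +0.4 to +0.7 in the middle of it. In the third row, responding visits supplied 65% to 73% of stimulation readings but only 46% to 47% of steps.

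**4. False positives with no true effect.** A mixed model with a participant intercept (drift SD 8, correlation 0.9; 60 trials) gave +0.57 mmHg (SE 0.14). It was significant in 23% of trials, and significantly positive in 22%, where 2.5% is nominal (simulation error √(0.22 × 0.78/60) = 5 points). Nearly all rejections were positive, so this is a shift and not only an understated standard error. With independent error the figures were -0.08 (SE 0.08) and 2%. A separate set of runs under drift gave 17% to 27% false positives with all readings and 1% to 5% with the first reading per step.

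**5. Does a session term help?** With a true mean slope of 10 per 100 mA that varies between sessions, all readings gave about 12.4 under the SAP's random structure and first readings alone 6.3 to 8.0. Slopes estimated within session gave 9.8 to 10.7 with either set. First readings run low because strongly responding sessions reach target and stop early, leaving the high currents to non-responders. In site comparisons, variable sites were favoured by 1.2 mmHg using all readings and penalised by 1.2 using first readings.

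**6. Cohen's d.** With no true effect, 2% to 18% of simulated visits reached a hold. There, the three triggering readings averaged 16 to 21 mmHg above baseline; the hold averaged 4.5 (independent error) or 11 to 14 (drift).

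**The case against.** The SAP never says that all readings are pooled; it leaves the stream and summary open. It also includes current and site as fixed effects. Holds occur at higher currents, so a raw mean rises without any model bias. With a common true slope of 10 per 100 mA, the raw mean was 7.1 against 5.5 (the average over 10 to 100 mA), yet a participant, site and current fit returned 10.0. A common upward shift also cancels between sites. Finally, keeping only the first reading exchanges one bias for another of similar size and leaves no spread for Cohen's d.

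All of this stands, and it rules out three stronger readings:

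- A reader might infer that stimulation must look effective even when it does nothing. The documents do not support that: with independent errors and one common effect the bias is zero, and they give no variance or correlation figures.
- A reader might take the pooled on-off contrast in the mixed-response runs (8.1 to 9.2 mmHg against a true 4.4 to 4.7) as the planned model's error. It is not, because that model adjusts for current.
- A reader might think any rise brings the 10-minute hold. Only SBP in the target range does.

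The objection does not dispose of the case where responses differ between sessions. There the current-adjusted fit is itself too steep, and the Protocol expects responses to vary by site and amplitude. Nor is the silence harmless: the power statement counts repeated readings, and no text equalises them. The mapping-visit section mentions five minutes before, during and after stimulation, but does not tie that period to a step.

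**Conclusion.** The point holds conditionally. Outcome-dependent sampling follows directly from the tree, and nothing in the SAP corrects for it. Where SBP drifts over minutes (the tree itself allows for drift during the hold) or responses differ by site within a participant, stimulation effects and site comparisons can be overstated and false positives inflated. Working sizes are roughly +0.4 to +0.7 mmHg with no true effect under drift, and a slope of about 12 against 10 per 100 mA with session-varying response, reaching 15 in the starker half-responder setting. These matter beside a claimed detectable difference under 2 mmHg. Every size rests on assumed SDs and correlations. Under drift with a common effect, the current slope erred in either direction (-0.9 to +0.8 mmHg per 100 mA), so the direction is not guaranteed for every estimate.

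**What to change.** SAP text only; the ramp and its stopping rules are unchanged.

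1. Name one SBP stream and one equal analysis window, fixed in advance, for each participant, site and current step. Define baseline as the mean of the 5-minute pre-stimulation period. A plain mean of however many readings a step has is not neutral: it ran 0.2 to 2.9 mmHg low.
2. Add a participant-by-site (session) random intercept and random slope for current (12 × 4 = 48 sessions), and allow for serial correlation. Confirm that the named R package can fit this. The session terms are essential: an equal window with participant as the only random effect is biased low through the ramp stop.
3. Report the 10-minute hold separately as durability. Base each participant's Cohen's d on hold or finger-trace data, not on the readings that triggered the hold. This reduces selection without removing it (working, step 6), so describe d as measured at a selected setting.
4. Rerun the simr power calculation under the decision tree with this model, report the SD and intraclass correlation used, and restate the power figure.

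The cost is rewriting and one simulation, wider intervals, and probably a less favourable stated power.

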Amplitude Parameter Mapping Visits 2-8: Before TSCS, electrodes will be placed on the vertebral midline at the spinous process (T7/8, T9/10, T11/12, L1/2), and the active site will be randomized. Each visit, we will complete one electrode placement site. Amplitude ramping will start at 10mA, with 10mA increments (pulse width, 1ms, frequency 30 Hz as shown (13)). Continuous real-time BP and heart rate will be measured for 5-minutes, before, during and after stimulation. During ramping, amplitude will stop increasing when SBP reaches optimal SBP between 110-120 mmHg (100-120 mmHg females) or reaches 100 mA with no SBP response (see below TSCS decision Tree). Amplitude will be decreased in 10 mA decrements in stimulation. BP will be continuously recorded during the rest period. Bilateral muscle activation (rectus femoris, medial hamstring, and gastrocnemius) will be monitored during all experiments to determine if skeletal muscle contractions are contributing to increases in BP. Additionally, signs and symptoms of autonomic dysreflexia will be monitored during TSCS testing in visits 3-6 by a questionnaire (**Appendix**). After every incremental increase of amplitude, investigator will ask participant if he/she is experiencing any symptoms. Maximum ramping amplitude will be 100 mA and testing will be halted if participant experiences any discomfort during testing. Based on preliminary work, regulation of neuromodulation of BP will occur at stimulation levels less than 100mA.

Participants will be notified by investigator if any of the findings from this study will affect the participants' health or welfare.

- Cardiovascular Assessments: While the subject is seated 3 ECG electrodes will be affixed to the chest and abdomen for continuous monitoring of HR and respiration rate (RR). Brachial BP will be monitored at 1 minute intervals using a standard adult BP cuff placed at the right upper arm, and beat-to-beat finger arteriolar BP will be continuously monitored from the right

middle finger throughout testing. Mean arterial pressure (mmHg) will be calculated from brachial BP using the formula: [systolic BP + (2\* diastolic BP)]/3. Beat-to-beat HR, RR and BP data will be viewed in real-time and stored for subsequent analysis using customized programs created with LabView graphical software.

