**3. Reach a stimulation intensity of 100 mA without a blood pressure response or intolerable symptoms.**

### **Risk and Discomforts:**

- Heart Rate, Arterial Stiffness and Blood Pressure: These are non-invasive procedures that involve minimal risk; however, some participants may experience discomfort when the ECG electrodes are removed from the skin and when the blood pressure cuffs are inflated.
- Transcutaneous stimulation: Participants may get headaches, autonomic dysreflexia, skin breakdown at the electrode placement site, pain, severe contractures (fractures) and muscle tears. If any of these potential risks occur, the stimulation will cease immediately and the investigators will monitor the situation.

As with any research, there may be unforeseen risks and discomforts. [name], a medical doctor associated with the study, will be available and present during testing to for clinical intervention if necessary or to treat any medical emergency.

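### The current-ramp tree gives no action for symptom-free systolic BP above 120 mmHg, item vi can raise current above target, and item vii raises it in women still within theirs

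*Protocol*

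**What the plan says.** The protocol's decision tree (TSCS Blood Pressure (BP) decision tree) opens: "Intensity ramp starting at 10 mA and increasing at 10 mA intervals until". Three stops follow:

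- **Stop 1:** the participant cannot tolerate the stimulation.
- **Stop 2:** three or more manual systolic readings in the target range (men 110-120 mmHg, women 100-120 mmHg).
- **Stop 3:** "Reach a stimulation intensity of 100 mA without a blood pressure response or intolerable symptoms".

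Under stop 2, items i to v take up to three readings and act on a sustained 10 mmHg rise. Below 100 mmHg (women 90) current goes up 10 mA. Below 110 (women 100) it goes up 5 mA. In range, the ramp stops for a 10-minute hold. Item vi covers a rise that is not sustained: if "only 1 or 2 readings that are 10 mmHg above baseline continue incremental ramp at 10 mA". Item vii covers the hold: if "during the 10-minute assessment systolic BP drifts down to < 110 but > 100, continue ramp at 5 mA". Item viii adds 10 mA if pressure drifts below 100. Items vii and viii carry no separate value for women.

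The narrative in Methods & Procedures (Amplitude Parameter Mapping) says "amplitude will stop increasing when SBP reaches optimal SBP between 110-120 mmHg (100-120 mmHg females"), and refers the reader to the tree.

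The SAP computes Cohen's d, with confidence intervals, at each participant's optimal parameters against baseline.

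**The concern.** A titration rule should state an action for every reading that can occur. This one covers pressures below and within target and, in the hold, downward drift only. Where pressure overshoots, staff either find no instruction or, under item vi, find an instruction to increase.

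The population makes this matter. Enrolment is of injuries at or above T6. The Review of Literature attributes BP instability, including autonomic dysreflexia, to lesions above T6, and Risk and Discomforts lists dysreflexia as a risk of stimulation.

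The chosen setting is also used later. It determines the SAP's Cohen's d and, by the Abstract, the tilt comparison with and without optimal stimulation.

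**Working it through.** The plan states no figure to reproduce here, so the check walks the tree by sex, baseline and readings. The example readings are illustrations.

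**1. Above 120 mmHg with no symptoms**
- Man, baseline 109, readings 122, 121, 122. The response threshold is 109 + 10 = 119, so all three count as a sustained rise. Items iii and iv need values below 110, and item v needs 110-120. No branch applies.
- Woman, baseline 95, readings 122, 124, 125. The threshold is 105. Again no branch applies.
- Stops 1 and 2 are not met. Stop 3 requires 100 mA without a response, and these participants have responded. What remains is the narrative's 100 mA maximum. From 50 mA (the current in Hypothesis 1) that leaves (100 - 50)/10 = 5 further steps; from 10 mA, (100 - 10)/10 = 9.
- In the hold, items vii and viii address falls only.

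**2. Item vi above target**
- The inclusion criterion joins systolic below 110 and diastolic below 70 with and/or, so a man at 115 systolic with diastolic below 70 meets it.
- His threshold is 115 + 10 = 125. Readings of 126, 126 and 124 give two at or above it, so item vi orders +10 mA although all three exceed 120.
- In general, b + 10 > 120 whenever b > 110. From such a baseline, any reading that triggers item i is already above target.

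**3. Item vi within target**
- Man, baseline 108, readings 119, 119, 117. The threshold is 118. Two readings reach it, so item vi says +10 mA. All three lie in 110-120, so stop 2 and the narrative say stop. No precedence is stated.

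**4. Missing female values in the hold**

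| Woman's systolic BP | Position | Ramp items iii-v | Hold items vii-viii |
|---|---|---|---|
| 101-109 | in target | stop (v) | +5 mA (vii) |
| 90-99 | below target | +5 mA (iv) | +10 mA (viii) |

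Exactly 100 mmHg falls under neither vii (above 100) nor viii (below 100), for either sex.

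**5. How readily readings above 120 arise**

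The documents give no reading-to-reading SD. Assume independent normal readings with SD 3, 5 or 8 mmHg and a man whose true systolic BP is 115.
- One reading above 120: p = 1 - Φ(5/SD) = 0.048, 0.159, 0.266.
- At least one of three: 1 - (1 - p)³ = 14%, 40%, 60%.

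This is the chance of meeting a reading the tree does not address. It is not the chance that current rises or that anyone is harmed.

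The same assumptions bear on how strict the repair should be. In a 10-reading hold, two consecutive readings above 120 occur in about 2%, 18% and 43% of cases; three consecutive occur in about 0.1%, 3% and 11%. A step-down triggered by three readings therefore disturbs far fewer men who are truly on target.

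**6. The optimal setting**

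Within a site, the tree sets the current: the first level with three in-range readings, then the hold. Between sites, the protocol's Transcutaneous spinal cord stimulation paragraph gives a goal (raise BP, reduce orthostatic symptoms) and no rule. The SAP's mixed model asks which parameters consistently raise pressure across participants; it does not pick one setting for each person.

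**The case against.** The strongest defence is that staff would not raise current in someone already in range. Stop 2 requires only three in-range readings, with no 10 mmHg condition, and the narrative stops the ramp once the range is reached. That stands. A reader might infer that the tree always pushes current up in participants who start or arrive in target; the documents do not support this. For in-range readings under item vi the fault is an unresolved conflict. It does not extend to readings above 120, on which stop 2 and the narrative are silent, or to item vii, which explicitly orders an increase.

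A reader might also infer that participants are unprotected. They are not: "After every incremental increase of amplitude, investigator will ask participant if he/she is experiencing any symptoms", BP is viewed in real time, discomfort halts testing, current is capped at 100 mA, a physician is present, and stimulation ceases if dysreflexia occurs. These make harm less likely. None tells the operator what to do at a symptom-free 126 mmHg.

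The evidence that a further step would raise pressure more is thin. The progressive rise in Preliminary Studies came from one participant stimulated at C7-T1, which is not one of the four study sites.

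On the SAP, a reader might infer that Cohen's d is inflated as if the best of every site-by-current combination were picked. The design does not work that way, because each ramp stops at the first sustained in-range current. Nor would choosing a setting from mapping by itself inflate the tilt comparison, whose stimulated readings are taken separately.

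**Conclusion.** The point holds as a fault in trial conduct and safety, and it should be corrected. As written, the tree has no action for symptom-free systolic BP above 120 mmHg; item vi can order 10 mA more at any pressure; and items vii and viii apply male thresholds to women. The first two gaps can occur in either sex. The third affects women at 101-109 mmHg (an increase while in target) and at 90-99 mmHg (10 mA where the ramp would give 5). These conclusions rest on the text alone; only the percentages depend on assumed SDs. The existing safeguards reduce the consequence without closing the gap.

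The SAP point is secondary: a missing rule for choosing among sites and other settings. Cohen's d is computed on the data used to choose the setting, so it can only be descriptive. The mixed model is not in question.

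**What to change.** **Protocol, decision tree, stop 2**

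- Add a branch: *If any systolic BP is > 120 mmHg, in the ramp or the hold, do not increase current and repeat at 1 minute. If 3 consecutive readings are > 120, step down 5 mA and reassess. Ramping may resume under items iii-viii if systolic BP later falls below target. If pre-stimulation systolic BP is > 120 mmHg, do not ramp at that visit.*
- Item vi: apply only when readings are below the target range. State that stop 2 and the narrative stop take precedence.
- Item vii: make the male lower bound ≥ 100 and add *(females: < 100 but ≥ 90)*.
- Item viii: add *(females: < 90)*.

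**SAP**

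- Before analysis, fix the selection rule. For example: among settings that met stop 2 and completed the 10-minute hold, take the one with most hold readings in range, then the lowest current.
- Report participants with no qualifying setting separately. A participant who starts in range can meet stop 2 without any rise, so identify these too.
- Label Cohen's d descriptive. Leave the mixed model as it is.

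**Cost.** A short protocol amendment and a few SAP lines, with no added visits or participants. Some ramps will stop earlier, so fewer high-current readings enter the model. If mapping is already complete, only the SAP changes apply.

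### The hold steps of the titration tree omit the female limits, so a woman already in her target range is told to add current; no step covers systolic BP above 120 mmHg

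*Protocol*

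**What the plan says.** The decision tree (Protocol, TSCS Blood Pressure decision tree, item 2) treats the response as sustained when there are "3 or more manual systolic BP within the target range", and sets that range separately by sex: 110–120 mmHg for men, 100–120 mmHg for women.

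The ramp steps keep the distinction:

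- Step iii: "still 10 mmHg - but < 100 mmHg (< 90 females mmHg) increase by 10 mA and repeat manual BP assessments"
- Step iv: "still 10 mmHg - but < 110 mmHg (< 100 mmHg females) increase by 5 mA and repeat manual BP assessment"
- Step v: "between 110-120 mmHg (100-120 mmHg females) stop intensity ramp and monitor BP for 10 minutes at that mA ramp"

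The steps that govern the 10-minute hold do not:

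- Step vii: "during the 10-minute assessment systolic BP drifts down to < 110 but > 100, continue ramp at 5 mA"
- Step viii: "during the 10-minute assessment systolic BP drifts down to < 100, continue ramp at 10 mA"

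The Methods text on amplitude mapping (Visits 2–8) repeats the sex-specific stop: "amplitude will stop increasing when SBP reaches optimal SBP between 110-120 mmHg (100-120 mmHg females". None of steps i to viii mentions a systolic pressure above 120 mmHg.

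**The concern.** Steps vii and viii are the only ones written for the hold, and their limits (110 and 100) are the male limits of steps iv and iii. For a woman they contradict step v and the Methods text: one place tells the operator to stop and hold, another to keep raising the current, for the same reading. Two operators who both follow the protocol could act differently.

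This affects three things:

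- **Exposure.** A woman may receive more current, over a longer session, than her stated target requires.
- **The individual map.** The objective is to find each participant's best parameters, and the SAP computes an effect size at each participant's optimal settings. If a woman's ramp ends too high, the current recorded for her can be too high as well.
- **Safety above target.** Participants are injured at or above T6, and autonomic dysreflexia is a listed risk. The tree gives no numerical action once systolic pressure passes 120 mmHg.

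**Working it through.** The plan states no figure for this point, so the check applies the written rules literally.

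**1. Map of actions for a woman.** It is assumed that all three readings are at least 10 mmHg above baseline.

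| Systolic BP (mmHg) | Ramp steps iii–v (female limits) | Hold steps vii–viii as written | Consistent? |
|---|---|---|---|
| below 90 | +10 mA | +10 mA | yes |
| 90–99 | +5 mA | +10 mA | no |
| 100 | stop and hold | no rule (in target, so harmless) | – |
| 101–109 | stop and hold | +5 mA | no |
| 110–120 | stop and hold | stay | yes |
| above 120 | no rule | no rule | gap |

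The female target 100–120 contains 21 whole-number values. Nine of them (101–109) trigger an increase: 9/21 = 0.43. For men the count is 0 of the 11 values in 110–120. These are counts of values, not probabilities.

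**2. Boundary in men.** Step vii requires more than 100 and step viii less than 100, so a hold reading of exactly 100 has no rule. Step iv would give +5 mA.

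**3. Outer bound on extra current.** Take the hypothesised 50 mA (Hypotheses, item 1) as the current at which a woman is first held, and 100 mA as the maximum. If her pressure stayed at 101–109 throughout, (100 − 50)/5 = 10 further steps would follow, each preceded by a hold of up to 10 minutes. This requires an almost flat response.

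**4. Likely size, under assumptions.** The documents give no response slope, reading variability or female baseline distribution. The simulation therefore used assumed inputs:

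- Baseline 85, 90 or 95 mmHg; linear rise 0.2, 0.3 or 0.5 mmHg per mA; reading SD 5 or 8 mmHg; serial correlation 0 or 0.5. That is 3 × 3 × 2 × 2 = 36 settings, with 1,500 runs each.
- One reading per current step, with a second and third only if at least 10 mmHg above the mean of five baseline readings (steps i–ii).
- Mean of three readings below 90: +10 mA; 90–99: +5 mA; 100–120: hold of 10 readings; above 120: assumed stop.
- Hold judged by the lower of two 5-minute means; cap 100 mA; the same errors under both rules.

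Extra final current is the result with vii–viii as written minus the result with female limits. It depends on how the drift wording is read:

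| Reading of the drift condition | Mean extra mA, range over settings (median) | Share of ramps with any extra current |
|---|---|---|
| must cross the limit from above | 1.3–9.6 (3.2) | 0.25–0.48 |
| any fall during the hold counts | 4.9–15.7 (10.1) | 0.41–0.79 |
| no fall needed | 5.7–27.1 (14.0) | 0.43–0.99 |

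The last row departs from the ordinary sense of the step and is only an outer bound.

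**5. Two response tests.** The item 2 heading and the Methods text test whether pressure is in range. Steps i–ii and vi test a rise of 10 mmHg over baseline; step vi, for example, says that with "only 1 or 2 readings that are 10 mmHg above baseline continue incremental ramp at 10 mA". Entry on diastolic pressure below 70 alone is allowed, so a baseline systolic above 110 is possible. At 110, 110 + 10 = 120 and both tests can just be met. At 111, 111 + 10 = 121, which exceeds 120, and they cannot both be met. The text does not say which governs.

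**The case against.** The best defence is that steps vii and viii carry no sex label, while the female target is stated three times: in the item 2 heading, in step v and in the Methods text. An operator has an explicit female stop rule, and a sensible one would follow it. That makes this a drafting omission, but it does not remove the conflict: the only instructions specific to the hold still say to add current.

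The size is also open to challenge, and much of that challenge stands. Ten extra steps is hard to reconcile with a rising response. At the assumed slopes, going from 101 to 110 mmHg takes 9/0.2 = 45, 9/0.3 = 30 or 9/0.5 = 18 mA, which is about 9, 6 or 4 steps. Under the strictest reading, the median mean excess (3.2 mA) is less than one 5-mA step. The SAP models current as a fixed effect with repeated readings, so extra steps mainly add observations; no bias in the primary mixed model has been shown.

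On pressure above 120, the Methods text can be read as already ending increases once the target is reached. Symptoms are asked about at every increment, stimulation ceases if dysreflexia occurs, and a physician is present. At the assumed slopes a 10 mA step adds only 2–5 mmHg on average. These points make the gap secondary, but they do not close it. None of these stops carries a systolic value. The Methods text halts for any discomfort, while item 1 of the tree allows 5 mA increments if discomfort is tolerable. The dysreflexia questionnaire is specified for visits 3–6, while mapping runs over visits 2–8.

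**Conclusion.** The concern holds. As written, the hold steps give a woman the wrong action at 101–109 mmHg (5 mA more while in target) and a larger increment than the ramp steps at 90–99 mmHg (10 mA instead of 5). That follows from the text alone.

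How much extra current results is uncertain: a mean of roughly 1 to 16 mA under the two ordinary readings of the drift condition, resting entirely on the assumed inputs above. The number of women among the 12 is not given and could be zero, in which case the error has no effect on this trial. The missing action above 120 mmHg is a secondary safety point, partly covered by other stops; how many participants would exceed 120 is likewise unknown and could be none. The conflict between the two response tests needs only clarification. The correction to vii and viii should be made on its own merits.

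**What to change.** Amend the decision tree as follows:

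- **Step vii:** below 110 but at least 100 (females: below 100 but at least 90), continue the ramp at 5 mA.
- **Step viii:** below 100 (females: below 90), continue the ramp at 10 mA.
- **New step:** if systolic pressure is sustained above 120, do not increase; hold or step down. The exact threshold is for the sponsor to set.
- **Clarifying sentence:** state whether the in-range test or the 10 mmHg rise governs when baseline systolic pressure is above 110.

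Using at least 100 in step vii also gives men a rule at exactly 100 and matches step iv. With the two line edits, no in-target value leads to more current in either sex.

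The cost is two line edits, one added step and one sentence. Eligibility, visits, sample size and the SAP are unchanged. A possible downside is fewer observations at high current in women.
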